5. STUDY POPULATION

The study population will include all highly sensitized kidney transplant candidates on the waitlist for more than 24 months at UW. A preliminary query of the Transplant Database indicates more than 40 candidates who are eligible for this study. This study will enroll 10 subjects.

5.1 Inclusion Criteria

Each patient must meet all of the following inclusion criteria to be enrolled in the study:

1. Male or female patients 18-70 years of age.
2. Able to provide informed consent.
3. Female patients who are postmenopausal for at least 1 year before the screening visit, or are surgically sterile, or If they are of childbearing potential, agree to practice 2 effective methods of contraception, at the same time, from the time of signing the informed consent

form through 30 days after the last dose of study drug, OR agree to practice true abstinence when this is in line with the preferred and usual lifestyle of the subject. (Periodic abstinence [eg, calendar, ovulation, symptothermal, post-ovulation methods] and withdrawal are not acceptable methods of contraception.)

4. Male patients, even if surgically sterilized (ie, status post-vasectomy), must agree to one of the following: Agree to practice effective barrier contraception during the entire study treatment period and through 30 days after the last dose of study drug, or Agree to practice true abstinence when this is in line with the preferred and usual lifestyle of the subject. (Periodic abstinence (eg, calendar, ovulation, symptothermal, post-ovulation methods] and withdrawal are not acceptable methods of contraception.)
5. Patients must be highly sensitized with a cPRA $\geq 80\%$
6. Be active on the waitlist for kidney transplantation > 24 months to confirm their inability to receive a deceased donor transplant because of their sensitization status.
7. Patients must meet the following clinical laboratory criteria:
 - Absolute neutrophil count (ANC) $\geq 1,000/\text{mm}^3$ and platelet count $\geq 75,000/\text{mm}^3$. Platelet transfusions to help patients meet eligibility criteria are not allowed within 3 days before study enrollment.
 - Hemoglobin higher than 6 g/dL
 - Total bilirubin $\leq 1.5 \times$ the upper limit of the normal range (ULN).
 - Alanine aminotransferase (ALT) and aspartate aminotransferase (AST) $\leq 3 \times$ ULN.

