Patients will be recruited from our center. All patients must be **(1)** Male or female patients 18-70 years of age **(2)** Able to provide informed consent **(3)** Female patients who are postmenopausal for at least 1 year before the screening visit, or are surgically sterile, or If they are of childbearing potential, agree to practice 2 effective methods of contraception, at the same time, from the time of signing the informed consent form through 90 days after the last dose of study drug, OR agree to practice true abstinence when this is in line with the preferred and usual lifestyle of the subject. (Periodic abstinence [eg, calendar, ovulation, symptothermal, post-ovulation methods] and withdrawal are not acceptable methods of contraception.) **(4)** Male patients, even if surgically sterilized (ie, status post-vasectomy), must agree to one of the following: Agree to practice effective barrier contraception during the entire study treatment period and through 90 days after the last dose of study drug, or Agree to practice true abstinence when this is in line with the preferred and usual lifestyle of the subject. (Periodic abstinence (eg, calendar, ovulation, symptothermal, post-ovulation methods] and withdrawal are not acceptable methods of contraception.) **(5)** Patients must be highly sensitized with a cPRA $\geq 80\%$ **(6)** Be active on the waitlist for kidney transplantation > 24 months to confirm their inability to receive a deceased donor transplant because of their sensitization status **(7)** Patients must meet the following clinical laboratory criteria (a) Absolute neutrophil count (ANC) $\geq 1,000/\text{mm}^3$ and platelet count $\geq 75,000/\text{mm}^3$. Platelet transfusions to help patients meet eligibility criteria are not allowed within 21 days before study enrollment (b) Total bilirubin $\leq 1.5 \times$ the upper limit of the normal range (ULN) (c) Alanine aminotransferase (ALT) and aspartate aminotransferase (AST) $\leq 3 \times$ ULN.

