6.6 Precautions and Restrictions

Fluid deficit Fluid deficit should be corrected as per standard of care before initiation of treatment and during treatment.

Pregnancy

It is not known what effects ixazomib has on human pregnancy or development of the embryo or fetus. Therefore, female patients participating in this study should avoid becoming pregnant, and male patients should avoid impregnating a female partner. Nonsterilized female patients of reproductive age group and male patients should use effective methods of contraception through defined periods during and after study treatment as specified below.

Female patients must meet 1 of the following:

- Postmenopausal for at least 1 year before the screening visit, or
- Surgically sterile, or
- If they are of childbearing potential, agree to practice 2 effective methods of contraception from the time of signing of the informed consent form through 90 days after the last dose of study drug, or
- Agree to practice true abstinence, when this is in line with the preferred and usual lifestyle of the subject. (Periodic abstinence [eg, calendar, ovulation, symptothermal, postovulation methods] and withdrawal are not acceptable methods of contraception.)

Male patients, even if surgically sterilized (ie, status postvasectomy) must agree to 1 of the following:

- Practice effective barrier contraception during the entire study treatment period and through 90 days after the last dose of study drug, or
- Agree to practice true abstinence, when this is in line with the preferred and usual lifestyle of the subject. (Periodic abstinence [eg, calendar, ovulation, symptothermal, postovulation methods for the female partner] and withdrawal are not acceptable methods of contraception.)

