8.3 Procedures for Reporting Drug Exposure During Pregnancy and Birth Events

If a woman becomes pregnant or suspects that she is pregnant while participating in this study or within 90 days after the last dose, she must inform the investigator immediately and permanently discontinue study drug. The sponsor-investigator must immediately fax a completed Pregnancy Form to the Millennium Department of Pharmacovigilance or designee (see Section 8.2). The pregnancy must be followed for the final pregnancy outcome.

If a female partner of a male patient becomes pregnant during the male patient's participation in this study, the sponsor-investigator must also immediately fax a completed Pregnancy Form to the Millennium Department of Pharmacovigilance or designee (see Section 8.2). Every effort should be made to follow the pregnancy for the final pregnancy outcome.

Suggested Pregnancy Reporting Form:

- Pregnancy Report Form (provided by Millennium)

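### Section 5.1 sets contraception at 30 days after the last dose for women and men, while the Protocol Summary and section 6.6 require 90 days

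*Combined protocol and SAP*

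**What the plan says.** The protocol states the length of post-treatment contraception in three places and relies on it in a fourth.

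- **Section 5.1, criterion 3 (women of childbearing potential):** "form through 30 days after the last dose of study drug".
- **Section 5.1, criterion 4 (men):** "Agree to practice effective barrier contraception during the entire study treatment period and through 30 days after the last dose of study drug".
- **Protocol Summary, Study Population, criterion 3:** "from the time of signing the informed consent form through 90 days after the last dose of study drug".
- **Protocol Summary, Study Population, criterion 4:** "Agree to practice effective barrier contraception during the entire study treatment period and through 90 days after the last dose of study drug".
- **Section 6.6 (women):** "signing of the informed consent form through 90 days after the last dose of study drug".
- **Section 6.6 (men):** "Practice effective barrier contraception during the entire study treatment period and through 90 days after the last dose of study drug".
- **Section 8.3 (pregnancy reporting by a female participant):** "while participating in this study or within 90 days after the last dose".

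True abstinence is accepted instead of contraception in all three places that state the rule, and women who are postmenopausal or surgically sterile are exempt. For partner pregnancies, section 8.3 refers only to the period of the male patient's participation and gives no number of days.

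**The concern.** One rule has two values, and the shorter one stands in the list that every patient must satisfy in order to enroll. Section 1.10 has the principal investigator sign an eligibility checklist before drug is dispensed, and it counts compliance with eligibility and with the contraception requirements among the ways risk is kept down. A checklist drafted from section 5.1 would record agreement to 30 days.

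What is at stake is fetal exposure. Section 6.6 states: "It is not known what effects ixazomib has on human pregnancy or development of the embryo or fetus". A patient guided by section 5.1 alone could stop contraception 60 days before section 6.6 allows. The schedule of events marks a pregnancy test at screening only and has no routine visit near 90 days after the last dose.

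**Working it through.** No sample-size, power or error-rate figure is involved, so the check is a comparison of texts followed by calendar arithmetic.

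**Step 1: the statements side by side.**

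| Place | Women | Men |
|---|---|---|
| Section 5.1 | 30 days | 30 days |
| Protocol Summary | 90 days | 90 days |
| Section 6.6 | 90 days | 90 days |
| Section 8.3 (reporting) | 90 days | no number given |

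Thirty days appears only in section 5.1. The document contains no amendment log that would explain the difference. The gap is 90 − 30 = 60 days for each sex.

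**Step 2: calendar days on the nominal schedule.** There are twelve 28-day cycles with doses on days 1, 8 and 15 (section 6.2).

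- Last dose: 1 + 11 × 28 + 14 = day 323, which reproduces Table 2-1(b).
- End of contraception under section 5.1: 323 + 30 = day 353.
- End under section 6.6: 323 + 90 = day 413.

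**Step 3: position of the last routine visit.** The protocol dates this visit in two ways.

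- Day 373 (section 4.3): 373 − 323 = 50 days after the last dose, and 413 − 373 = 40 days before the 90-day period ends.
- One month after the last dose (section 6.2 and the Table 2-1(b) column heading), with a month taken as 30 days: day 353, and 413 − 353 = 60 days before the period ends.

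On either reading the visit comes before the 90 days are over. Dose delays or early stopping shift all these days, so the period has to be counted from the actual last dose.

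**Step 4: are the two figures interchangeable in exposure?** This is context only. Section 1.4 gives a terminal half-life of 9.5 days. Assuming simple first-order decay, the fraction remaining is 0.5^(30/9.5) = 0.112, or about 11%, at 30 days, and 0.5^(90/9.5) = 0.0014, or about 0.14%, at 90 days. The documents give no exposure threshold for fetal risk, so this does not estimate harm.

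**Step 5: the separate platelet mismatch.** The Protocol Summary bars platelet transfusions given to meet eligibility within 21 days before enrollment; section 5.1 says 3 days. A patient transfused more than 3 and up to 21 days before enrollment is eligible under one text and not the other, a band of 21 − 3 = 18 days. Sections 6.4 and 6.5 also say 3 days, but before each dosing day. Scheduled doses are 7, 7 and then 14 days apart (days 1, 8, 15, 29), so the longest gap is 14 days. A 21-day rule there would place every day from first to last dose inside the barred window. It would also clash with the allowance in section 6.5 for transfusion when clinically indicated.

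**The case against.** The strongest reply is that the 90-day rule is already in force. Section 6.6 governs conduct during and after treatment, section 5.1 only records what a patient agrees to at entry, and a patient who follows the whole protocol uses contraception for 90 days. That is correct. It makes this a drafting inconsistency rather than a missing safeguard, but it does not reconcile the two numbers.

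A reader might be tempted by several stronger readings, which the documents do not support.

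- **Patients were told 30 days.** The consent pages are not in the public document and the checklist is not shown. Which figure reached patients cannot be determined, so stopping early is a possibility and not a demonstrated event.
- **Nothing later would reveal a pregnancy.** This goes too far. Section 8.3 obliges a woman who becomes pregnant, or suspects it, within 90 days of her last dose to tell the investigator at once. What is absent is a scheduled test after screening or a routine visit near day 90.
- **Partner pregnancies go unreported for 40 to 60 days.** That requires a man's participation to end at the final visit, which the protocol does not define. For men who are transplanted, data are collected for 6 months after surgery, so participation may last longer. What stands is that section 8.3 gives no end date matching the 90 days asked of men in section 6.6.
- **Section 4.1 recruits patients who are not highly sensitized.** Its first recruitment bullet does say cPRA below 80%. The next bullet has the sign the right way round, and criterion 5 of section 5.1 controls entry, so this is a clerical slip.

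**Conclusion.** The contradiction holds and should be fixed. Criteria 3 and 4 of section 5.1 understate post-treatment contraception by 60 days for both sexes, relative to the Protocol Summary, section 6.6 and, for women, the reporting window in section 8.3. The weight of the text favors 90 days as the intended figure.

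The day counts assume the nominal schedule with no delays. The issue touches only women of childbearing potential and men who rely on contraception rather than abstinence; how many of the 10 patients that is cannot be known from the documents. No efficacy, power or sample-size result changes, and no fetal-risk estimate is made. The platelet mismatch is a separate and smaller eligibility conflict, confined to the Protocol Summary and section 5.1.

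**What to change.** 1. In section 5.1, criteria 3 and 4, change 30 days to 90 days.
2. Confirm that the eligibility checklist and patient information say 90 days, counted from the actual last dose. The existing final or early termination visit is a natural point to remind patients of the time remaining.
3. In section 8.3, state that partner pregnancies are reportable through 90 days after the male patient's last dose.
4. If 30 days was truly intended, justify it and amend the Protocol Summary and sections 6.6 and 8.3 instead.
5. Separately, have the sponsor confirm 3 or 21 days for platelet transfusion before enrollment and use that value in the Protocol Summary and section 5.1 only. Leave the 3-day rule before each dosing day in sections 6.4 and 6.5 as it is.
6. Correct the cPRA sign in the first recruitment bullet of section 4.1 to at least 80%.

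The cost is a wording amendment and a check of two site documents, with no added patients, visits or tests.

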5.2 Exclusion Criteria

Exclusion criteria: Patients will be excluded from the study based on the following criteria:

- (1) Female patients who are lactating or have a positive serum pregnancy test during the screening period
- (2) Major surgery requiring hospitalization within 6 months before enrollment
- (3) Infection requiring systemic antibiotic therapy or other serious infection within 14 days before study enrollment
- (4) Evidence of current uncontrolled cardiovascular conditions, including uncontrolled hypertension, uncontrolled cardiac arrhythmias, symptomatic congestive heart failure, unstable angina, or myocardial infarction within the past 6 months
- (5) Systemic treatment, within 14 days before the first dose of ixazomib, with strong CYP3A inducers (rifampin, rifapentine, rifabutin, carbamazepine, phenytoin, phenobarbital), or use of St. John's wort
- (6) Any serious medical or psychiatric illness that could, in the investigator's opinion, potentially interfere with the completion of treatment according to this protocol
- (7) Inability to take oral medication
- (8) Diagnosed or treated for another malignancy within 2 years before study enrollment or previously diagnosed with another malignancy and have any evidence of residual disease. Patients with nonmelanoma skin cancer or carcinoma in situ of any type are not excluded if they have undergone complete resection
- (9) Grade 2 or greater peripheral neuropathy according to NCI Common Terminology Criteria for Adverse Events (CTCAE)
- (10) Participation in other desensitization therapies or investigational drug clinical trials, including those with other investigational agents not included in this trial, within 6 months of the start of this trial and throughout the duration of this trial
- (11) Patients that have previously been treated with ixazomib, or participated in a study with ixazomib whether treated with ixazomib or not
- (12) Active or treated infection for HIV, HCV or HBV

- (13) History of Liver cirrhosis, biopsy confirmed
- (14) Elevated transaminases (greater than 3 times the upper limit of normal)
- (15) Known hypersensitivity to ixazomib
- (16) Active substance abuse by self-report or medical record
- (17) Electrocardiography evidence of acute ischemia or active conduction system abnormalities

6. STUDY DRUG

6.1 Description of Investigational Agents

Ixazomib Capsules. Provided by Millennium-Takeda. The ixazomib drug product is provided in strengths of 3.0-, and 2.3-mg and 0.5-, and capsules as the active boronic acid. The different dose strengths are differentiated by both capsule size and color as described below: For this study, we will initiate therapy with the 3 mg capsules according to the package insert information for patients with end-stage renal disease. For additional details, please see the ixazomib IB.

| Dose Strength | Capsule Size | Capsule Color |
|---------------|--------------|---------------|
| 3.0 mg | Size 3 | Light gray |
| 2.3 mg | Size 2 | Light pink |
| 0.5 mg | Size 3 | Dark green |

Dexamethasone tablets, Dexamethasone Tablets USP are available for oral administration containing either 0.5 mg, 0.75 mg, 1 mg, 1.5 mg, 2 mg, 4 mg or 6 mg of dexamethasone USP. For this study, we will use the 20 mg dose (5 tablets of 4 mg each). For additional information please refer to the attached IB for dexamethasone.

6.2 Study Drug Administration

- Ixazomib and dexamethasone will be taken based on the information in the package insert.
- The starting dose of ixazomib will be 3 mg taken orally on days 1, 8, and 15 of a 28-day cycle. The dose of dexamethasone will be 20 mg taken orally on the same days as ixazomib.
- Patients will take ixazomib and dexamethasone for twelve (12) 28-day cycles.
- Ixazomib should be taken once a week on the same day and at approximately the same time for the first three weeks of a four week cycle. Ixazomib should be taken at least one hour before or at least two hours after food. The whole capsule should be swallowed with water. The capsule should not be crushed, chewed or opened. If an ixazomib dose is delayed or missed, the dose should be taken only if the next scheduled dose is ≥ 72 hours away. A missed dose should not be taken within 72 hours of the next scheduled dose. A double dose should not be taken to make up for the missed dose. If vomiting occurs after taking a dose, the patient should not repeat the dose. The patient should resume dosing at the time of the next scheduled dose.
- Ixazomib and dexamethasone should not be taken at the same time, because dexamethasone should be taken with food and ixazomib should not be taken with food.
- Ixazomib and dexamethasone will be dispensed monthly by the PRC
- Diaries/logs will be used by patients to track their doses.

Treatment Plan and Laboratory Assessment. Participants will undergo a 12-month treatment

regimen of ixazomib-dexamethasone on days 1, 8, and 15 of a 28-day cycle, for 12 cycles (Table 1-1 below). The dose of ixazomib (3 mg) is based on packet information for patients with reduced kidney function and will be taken at least one hour before or at least two hours after food. The dose of dexamethasone is 50% lower than the dose recommended in the package insert to reduce the possibility of metabolic complications in ESRD.

Table 1-1 IXADES Treatment Protocol for desensitization

| 28-Day Cycle (a 4-week cycle) | | | | | | | | |
|-------------------------------|--------|----------|--------|-----------|--------|------------|--------|------------|
| | Week 1 | | Week 2 | | Week 3 | | Week 4 | |
| | Day 1 | Days 2-7 | Day 8 | Days 9-14 | Day 15 | Days 16-21 | Day 22 | Days 23-28 |
| Ixazomib (NINLARO) 3 mg | ✓ | | ✓ | | ✓ | | | |
| Dexamethasone 20 mg | ✓ | | ✓ | | ✓ | | | |

Duration of Treatment and Follow-up. All participants, those that receive a kidney transplant during the defined period and those that do not will be followed for the entire length of treatment, plus one month following the last dose of the study drug. All subjects will be asked to return for a final study visit approximately one month following the last dose of study drug. During this final study visit, subjects will undergo physical examination, bone marrow aspirate collection, CBC, LFT check, ECG and echocardiogram.

Bone Marrow Aspirate Collection Procedure: Subjects will be given the option of having the bone marrow aspirate performed under conscious sedation or local anesthetic only. The bone marrow aspirate will be collected in a transplant clinic room. If the bone marrow aspiration is done under conscious sedation, subjects will be given instructions to fast for six hours before the procedure (medications are allowed) and not to drive themselves home or operate dangerous equipment after the procedure.

Measurement of effect. We will determine the effect of ixazomib by measuring cPRA, whether patients receive a kidney transplant while participating in the study, antibody strength by MFI, and the toxicity (measured by the incidence of adverse events) of the treatment quarterly up to the end of the study.

Ixazomib Administration

All protocol-specific criteria for administration of study drug must be met and documented before drug administration. Study drug will be dispensed only to eligible patients by a member of the study team. Patients should be monitored for toxicity, as necessary, and doses of ixazomib should be modified as needed to accommodate patient tolerance to treatment; this may include symptomatic treatment, dose interruptions, and adjustments of ixazomib dose (see Section 6.3).

Capsules of ixazomib will also be referred to as study drug. Study drug will be supplied by Millennium as capsules 0.5, 2.3, and 3.0 mg ixazomib. The prescribed administration of ixazomib doses in this study is 9 mg ixazomib in a 28 day cycle. Patients should be instructed to swallow ixazomib capsules whole, with water, and not to break, chew, or open the capsules. Ixazomib should be taken on an empty stomach (no food or drink) at least 1 hour before or at least 2 hours after food. Each capsule should be swallowed separately with a sip of water. A total of approximately 8 ounces (240 mL) of water should be taken with the capsules.

Missed doses can be taken as soon as the patient remembers if the next scheduled dose is 72 hours or more away. A double dose should not be taken to make up for a missed dose. If the patient vomits after taking a dose, the patient should not repeat the dose but should resume dosing at the time of the next scheduled dose.

Ixazomib Destruction

Investigational ixazomib (expired or end of study) should be destroyed on site according to the institution's standard operating procedure. We will document removal and destruction on drug accountability logs.

Dexamethasone: 20 mg of dexamethasone (5 tablets of 4 mg each) will be taken with food on days 1, 8, and 15 of a 28 day cycle (same days as ixazomib).

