2. STUDY OBJECTIVES

2.1 Primary Objectives

Specific Aim 1. To determine the safety and efficacy of ixazomib as a desensitization strategy. 10 highly sensitized kidney transplant candidates on the waitlist for more than 24 months will receive ixazomib 3 mg (and dexamethasone 20 mg) on days 1, 8, and 15 of a 28 cycle for 12 months. The primary objective is to evaluate the safety (distal neuropathy, thrombocytopenia, and gastrointestinal symptoms) and efficacy (decline in cPRA > 20%) of ixazomib. The secondary efficacy endpoint is transplantation rate within 12 months of therapy.

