7. STATISTICAL AND QUANTITATIVE ANALYSES

7.1 Statistical Methods

More than 50% of patients with CDC T cell crossmatch titers $\geq 1:8$ and/or cPRA $> 80\%$ fail to respond to desensitization (5, 8). In this pilot exploratory, proof of concept, open-label, single-center phase II clinical trial, we hypothesize that our study will have a higher rate of transplantation. [name], PhD, epidemiologist and biostatistician in the division of nephrology, will perform the statistical analyses. *Primary* efficacy (decline in cPRA $> 20\%$) and safety (discontinuation of therapy due to adverse events) endpoint will be analyzed using the exact binomial test. The *secondary* endpoint (time to transplantation) will be assessed using Kaplan-Meier analyses and log rank tests. Baseline characteristics will be compared between participants with and without the primary end point using the 2-sample t test for continuous variables and the Fisher's exact test for categorical variables. Relationships between serum BAFF/APRIL, antibodies, and baseline cPRA will be assessed using the Pearson correlation coefficient. The influence of serum BAFF/APRIL, antibodies, and bone marrow plasma cells on end points of interest will be investigated using Kaplan-Meier curves and Cox proportional-hazards models.

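### Dexamethasone is planned on every ixazomib day in a single arm, but the objectives and effect measure credit ixazomib alone, and the safety terms leave open which drug's events and discontinuations count

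*Combined protocol and SAP*

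**What the plan says.** **Treatment.** Section 6.2 gives both drugs to everyone: "Patients will take ixazomib and dexamethasone for twelve (12) 28-day cycles". On timing it says: "The dose of dexamethasone will be 20 mg taken orally on the same days as ixazomib". The same section calls the treatment a "regimen of ixazomib-dexamethasone on days 1, 8, and 15 of a 28-day cycle, for 12 cycles". Sections 6.11 (treatment assignment) and 7.1.2 (randomization) are marked not applicable, so there is one arm and no group on either drug alone.

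**Attribution.** The hypothesis in Sections 1.1.1 and 1.9 is that ixazomib reduces DSA production and allows transplantation. Section 2.1, like Specific Aim 1 in the Protocol Summary, states: "The primary objective is to evaluate the safety (distal neuropathy, thrombocytopenia, and gastrointestinal symptoms) and efficacy", and the sentence ends by naming ixazomib only. The measurement-of-effect paragraph in Section 6.2 says: "We will determine the effect of ixazomib by measuring cPRA, whether patients receive a kidney transplant while participating in the study".

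**Safety terms.**
- Section 6.2: "Capsules of ixazomib will also be referred to as study drug". Section 6.1, however, describes dexamethasone among the investigational agents, and the drug-administration instructions in 6.2 cover both drugs.
- Section 8.2 asks about the relation of each SAE to all study drugs, with a single yes/no answer.
- Section 9.1 enters into OnCore only events judged related to the study drug (singular). Its last paragraph says all AEs and SAEs go into OnCore.
- Section 6.3.2 lists dexamethasone's own complications and allows it to be reduced or stopped separately.
- Section 7.1 gives the primary safety variable as "safety (discontinuation of therapy due to adverse events", without naming a drug.

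**The concern.** When two drugs are planned for everyone on the same days and there is no comparator, an outcome belongs to the pair. A fall in cPRA reported as an ixazomib effect, or a pattern of infections reported as ixazomib toxicity, would claim more than the clinical endpoints can show.

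The safety side matters more in practice, because it affects what is counted. Section 9.1 has the DMC reports built from OnCore. If study drug is read as ixazomib capsules and the related-only rule is followed, a non-serious event attributed to dexamethasone alone need not be entered, and the DMC would not see it in those reports. A patient who stops only dexamethasone because of an adverse event could be counted either way in the primary safety analysis.

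**Working it through.** **1. The plan's own figures (Section 7.1.1).** Inputs: n = 10, null success rate 0%, at least one success needed.
- P(at least 1 of 10 | true rate 0.2) = 1 − 0.8^10 = 0.893. The plan says more than 80%, which agrees.
- Exact (Clopper-Pearson) 95% CI for 3/10: 6.67% to 65.25%. The plan gives 6.7% to 65.2%, which agrees.

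**2. Planned overlap (Section 6.2).** 3 doses × 12 cycles = 36 planned doses of each drug, on the same days, over 12 × 28 = 336 days. Planned dexamethasone is 36 × 20 mg = 720 mg per patient. This is planned exposure; Section 6.3.2 lets actual exposure diverge.

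**3. What one success would show.** Let q be the chance that a patient meets the cPRA criterion with no contribution from ixazomib, through dexamethasone or background variation in cPRA. The documents give no value for q, so those below are assumptions. P(at least 1 of 10) = 1 − (1 − q)^10:

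| Assumed q | P(at least 1 of 10) |
|---|---|
| 0% | 0% |
| 1% | 9.6% |
| 2% | 18.3% |
| 5% | 40.1% |
| 10% | 65.1% |

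One success shows that responses occur on the regimen. It would point to ixazomib specifically only if q were taken to be zero.

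**4. Which adverse events reach the data.** Take a non-serious event judged due to dexamethasone alone.
- Study drug as ixazomib capsules (Section 6.2) plus the related-only rule (Section 9.1): not entered.
- Study drug as both agents (the sense of Sections 6.1 and 8.2) plus the related-only rule: entered.
- The closing paragraph of Section 9.1: entered whatever its cause.

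The text does not choose among these. For a serious event the Section 8.2 question covers both drugs, but one yes/no answer does not record which drug was suspected.

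**5. Which discontinuations count.** Assume, for illustration only, that two of the ten patients stop dexamethasone alone because of an adverse event and nobody stops ixazomib. Exact 95% limits are the 2.5% quantile of Beta(x, n − x + 1), taken as 0 when x = 0, and the 97.5% quantile of Beta(x + 1, n − x).
- Only ixazomib stops count: 0/10, CI 0% to 30.8% (upper limit 1 − 0.025^(1/10)).
- Either drug counts: 2/10, CI 2.5% to 55.6%.

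**The case against.** The strongest reply is that the protocol is more careful than the attribution wording suggests, and much of that reply stands.

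- A reader might infer that the causality rules credit ixazomib alone. They do not. Section 8.2 covers all study drugs for SAEs and any study drug for late SAEs. The defects are inconsistent terms and no answer per drug.
- A reader might infer that withdrawal for adverse events is tied to ixazomib. Section 7.1.10 refers to the whole of Section 6.3, which includes the dexamethasone rules in 6.3.2.
- A reader might infer that dexamethasone events will drop out of the safety result. Sections 3.1 and 7.1.8 list event types without attributing them to a drug, Section 8.1.1 defines AEs regardless of cause, and the end of Section 9.1 sends all of them to OnCore. Loss is possible only because Section 9.1 also says the opposite.
- A reader might infer that the conclusion in Section 7.1.1 is misattributed. It already refers to the proposed treatment, and Section 2.1 discloses the dexamethasone in describing the regimen.
- A reader might infer that the drugs are always taken together and that the study yields nothing specific to ixazomib. Section 6.2 separates the two within the day because of food, Section 6.3.2 allows exposure to diverge, and Section 3.3 plans in vitro work on ixazomib's direct effect on BAFF/APRIL in stromal cell cultures. That work does not isolate an effect on cPRA.

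It can also be said that a ten-patient proof-of-concept study need not separate its components. That is fair, and no comparator is asked for. None of this changes the ixazomib-only wording of the hypothesis, the primary objective and the effect measure, or settles the conflict in Section 9.1 or the undefined discontinuation in Section 7.1.

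**Conclusion.** The point holds as one of attribution and definition, and it should be fixed. The clinical endpoints support statements about ixazomib plus dexamethasone; the hypothesis, Section 2.1 and the effect measure in Section 6.2 promise statements about ixazomib. On safety, the documents leave two things undecided: whether non-serious events due to dexamethasone alone are entered, and whether stopping dexamethasone alone is a primary safety event.

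The size of any misattribution cannot be computed, because the documents give no response rate without ixazomib. The figures from 9.6% to 65.1% rest on assumed rates of 1% to 10%, and the 0/10 versus 2/10 contrast rests on an assumed two patients. They show how much turns on the wording and do not predict results. The design remains valid for the regimen, and the plan's stated interval and power are correct.

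**What to change.** 1. State the hypothesis (Sections 1.1.1 and 1.9), the primary objective (Protocol Summary and Section 2.1) and the measurement of effect (Section 6.2) as those of the ixazomib-dexamethasone regimen, and say that the clinical endpoints cannot separate the two drugs. Section 7.1.1 needs no change.
2. Define study drug once, so that in Section 9.1 it covers both drugs. Reconcile the two OnCore statements in that section so that all adverse events are entered, with relatedness recorded as an attribute of the event and not used as a condition for entry.
3. Record causality and discontinuation separately for ixazomib and dexamethasone.
4. State in Section 7.1 which discontinuation counts for the primary safety variable, and tabulate it by drug. Counting either drug is one workable choice; the documents do not dictate it.

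The cost is protocol wording, an extra CRF field for per-drug attribution, and a narrower claim. Sample size, power, dosing and stopping rules are unaffected.
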